**Table 1 Schedule of Events**

Study Assessment or Event	Screening and Enrollment*	End of Study Month ± 1 week							
		3	6	9	12	15	21	27	EoS g
Informed consent a	x								
Inclusion/Exclusion Criteria	x								
Complete physical exam b	x	x	x	x	x	x	x	x	x
Vital signs	x	x	x	x	x	x	x	x	x
12-Lead ECG	x	x	x	x	x	x	x	x	x
Clinical laboratory tests c	x	x	x	x	x	x	x	x	x
Pregnancy test d	x	x	x	x	x	x	x	x	x
Amifampridine Treatment		x	x	x	x	x	x	x	
QoL	x	x	x	x	x	x	x	x	x
Dispense IP e	x	x	x	x	x	x	x		
IP accountability		x	x	x	x	x	x	x	x
Adverse events/SAEs f	x	x	x	x	x	x	x	x	x
Concomitant medications	x	x	x	x	x	x	x	x	x

EoS= End of Study is the patients last visit to the site and discontinuation of study medication; IP=investigational product; QoL=quality of life; SAE=serious adverse event.

a Informed consent must be obtained before any study procedures are performed.

b Complete physical examination includes evaluation of all major body systems, including weight at all visits (Section 10.6.6).

c Clinical laboratory tests include serum chemistry, hematology, and urinalysis.

d Urine pregnancy tests will be obtained from female patients of childbearing potential.

e Pharmacist will dispense sufficient amount of medication until the next clinic visit. All unused medication must be returned to the clinic for drug accountability.

f SAE reporting commences after informed consent is signed. Non-serious adverse event reporting commences after the first dose of study drug for the current Long-Term Study.

g EoS or early termination visit if the last visit does not coincide the scheduled 3- or 6-month visit.

\*These data may be obtained from Study SMA-001. If data not available, then the assessment should be repeated.

	SMA-002	Page 20
---	---------	---------

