## 11 REPORTING ADVERSE EVENTS

### 11.1 Adverse Events

For this protocol, a reportable AE is any untoward medical occurrence (e.g. sign, symptom, illness, disease or injury) in a patient administered the IP or other protocol-imposed intervention, regardless of attribution. This includes:

- AEs not previously observed in the patient, that emerge during the study.
- Pre-existing medical conditions judged by the Investigator to have worsened in severity or frequency or changed in character during the study.
- Complications that occur as a result of non-drug protocol-imposed interventions.

An adverse drug reaction is any AE for which there is a reasonable possibility that the IP caused the AE. “Reasonable possibility” means there is evidence to suggest a causal relationship between the IP and the AE.

Whenever possible, it is preferable to record a diagnosis as the AE term rather than a series of terms relating to a diagnosis.

All ongoing non-serious AEs, even those which began under Protocol SMA-001, will be reported from the end of the double-blind study (SMA-001) or from Day 0 for those not randomized to double blind medication in SMA-001 through the termination visit or at the early termination visit and will be recorded on the AE page of the eCRF. All ongoing SAEs from SMA-001 will be reported. The criteria for determining, and the reporting of new SAEs is provided in Section 11.2.

The Investigator should follow all unresolved AEs until the events are resolved or stabilized, the patient is lost to follow-up, or it has been determined that the study treatment or participation is not the cause of the AE. Resolution of AEs (with dates) should be documented on the appropriate CRF page(s) and in the patient’s medical record.

The Investigator responsible for the care of the patient or qualified designee will assess AEs for severity, relationship to IP, and seriousness (refer to Section 11.2 for SAE definition). Severity (as in mild, moderate or severe headache) is not equivalent to seriousness, which is based on patient/event outcome or action criteria usually associated with events that pose a threat to a patient’s life or functioning. Seriousness (not severity) serves as a guide for defining regulatory reporting obligations.

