## 11.2 Serious Adverse Events

A serious adverse event is any untoward medical occurrence that at any dose meets 1 or more of the following criteria:

- Is fatal
- Is life threatening
  - *Note: Life-threatening refers to an event that places the patient at immediate risk of death. This definition does not include a reaction that, had it occurred in a more severe form, might have caused death*
- Requires or prolongs in-patient hospitalization

	SMA-002	Page 33
---	---------	---------

- Results in persistent or significant disability or incapacity
- Is a congenital anomaly or birth defect, that is, an AE that occurs in the child or fetus of a patient exposed to IP prior to conception or during pregnancy
- Is an important medical event or reaction.

The reporting period for SAEs begins after informed consent is obtained for the current SMA-002 study and continues through 4 weeks after the last visit.

Any SAE, whether or not considered related to study drug, must be reported within 24 hours of knowledge of the event by forwarding (fax, email) the study-specific SAE Report Form to Catalyst and its designee PhAST Consulting s.r.l.. The Investigator should not wait to collect information that fully documents the SAE before notifying Catalyst. As additional information becomes available, including but not limited to the outcome of the SAE and any medication or other therapeutic measures used to treat the event, it must be reported within 24 hours in a follow-up report.

The Investigator should follow all unresolved SAEs until the events are resolved or stabilized, the patient is lost to follow-up, or it has been determined that the study treatment or participation is not the cause of the AE. Resolution of AEs (with dates) should be documented in the CRF and in the patient's medical record.

For some SAEs, Catalyst or designee may follow up by telephone, fax, email, and/or a monitoring visit to obtain additional case details deemed necessary to appropriately evaluate the SAE report (e.g. hospital discharge summary, consultant report, autopsy report).

At the last scheduled visit, the Investigator should instruct each patient to report any subsequent SAEs that the patient's personal physician(s) believes might be related to prior study treatment.

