10.12.1 Adverse Events

For this protocol, a reportable AE is any untoward medical occurrence (e.g. sign, symptom, illness, disease or injury) in a patient administered the IP or other protocol-imposed intervention, regardless of attribution. This includes:

- AEs not previously observed in the patient, that emerge during the study.
- Pre-existing medical conditions judged by the Investigator to have worsened in severity or frequency or changed in character during the study.
- Complications that occur as a result of non-drug protocol-imposed interventions.

An adverse drug reaction is any AE for which there is a reasonable possibility that the IP caused the AE. “Reasonable possibility” means there is evidence to suggest a causal relationship between the IP and the AE.

Whenever possible, it is preferable to record a diagnosis as the AE term rather than a series of terms relating to a diagnosis.

All ongoing non-serious AEs, even those which began under SMA-001 study, will be reported from the end of the double-blind study (SMA-001) or from Day 0 for those not randomized to double blind medication in SMA-001 study through the termination visit or at the early termination visit and will be

recorded on the AE page of the eCRF. All ongoing SAEs from SMA-001 study will be reported. The criteria for determining, and the reporting of new SAEs is provided in Study Protocol Section 11.2.

The Investigator should follow all unresolved AEs until the events are resolved or stabilized, the patient is lost to follow-up, or it has been determined that the study treatment or participation is not the cause of the AE. Resolution of AEs (with dates) should be documented on the appropriate CRF page(s) and in the patient's medical record.

The Investigator responsible for the care of the patient or qualified designee will assess AEs for severity, relationship to IP, and seriousness (refer to Protocol Section 11.2 for SAE definition). Severity (as in mild, moderate or severe headache) is not equivalent to seriousness, which is based on patient/event outcome or action criteria usually associated with events that pose a threat to a patient's life or functioning. Seriousness (not severity) serves as a guide for defining regulatory reporting obligations.

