The Investigator will determine the severity of each AE using grades defined in [Table 1](#) (the event will be recorded on the source documents and AE CRF). Events that are Grades 4 and 5 are serious events and require completion of both an SAE form and AE CRF.

Table 1 - Categories of Severity for Adverse Events

Severity	Description	
Grade 1	Mild; asymptomatic or mild symptoms; clinical or diagnostic observations only; intervention not indicated.	
Grade 2	Moderate; minimal, local or noninvasive intervention indicated; limiting age-appropriate instrumental ADL*.	
Grade 3	Severe or medically significant but not immediately life-threatening; hospitalization or prolongation of hospitalization indicated; disabling; limiting self-care ADL**.	
Grade 4	Life-threatening consequences; urgent intervention indicated.	Note: Grade 4 and 5 adverse events should always be reported as serious adverse events
Grade 5	Death related to AE.	

Activities of Daily Living (ADL)

* Instrumental ADLs refer to preparing meals, shopping for groceries or clothes, using the telephone, managing money, etc.

** Self-care ADLs refer to bathing, dressing and undressing, feeding self, using the toilet, taking medications, and not bedridden.

A Treatment-Emergent Adverse Event (TEAE) is any AE that emerges after the first dose of study drug for the current Long-Term Study. All AEs will be coded using the Medical Dictionary for Regulatory Activities (MedDRA), Version 23.0. All TEAEs will be summarized. Counts and percentages will be presented for each observed System Organ Class (SOC) and Preferred Term (PT) as defined in MedDRA. A patient having more than one TEAE with the same PT will be counted only once in the incidence calculation for that PT. Similarly, if a patient has more than one TEAE in the same SOC, the patient will be counted only once in the total number of patients with a TEAE for that SOC. Each TEAE will be assessed with respect to severity and relationship to treatment. All AEs will be listed, regardless of whether they were study treatment related.

The relationship of an AE will be recorded using the specified relationship categories described in [Table 2](#).

Table 2 - Description of relationship to adverse events categories

Relationship Category	Description

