1.1 Weakness
1.2 Pain
1.3 Fatigue
1.4 Locking
1.5 Eyelids
1.6 Double vision
1.7 Swallowing
2.1 Activities
2.2 Independence
2.3 Social relationship
2.4 Emotions
2.5 Body imagine
2.6 QoL
3.1 Perceived treatment
3.2 Expected treatment

Listing 16.2.5.1. Treatment Emergent Adverse Events

Site	Patient	System Organ Class	Preferred Term	Verbatim Term	SAE (1)	Was AE started in SMA-001 study?	Start date	End date	Ongoing (2)	Duration (3)	Severity (4)	Relations hip (5)	Action taken (6)	Outcome (7)	Date of death
xxx	xxx	xxxxxx	xxxxxx	xxxxxx	xxx	No	DDMMYYYY	DDMMYYYY	No	xxxxx	xxxxx	xxxxx	xxxxx	xxxxx	xxxxx
		xxxxxx	xxxxxx	xxxxxx	xxx	No	DDMMYYYY	DDMMYYYY	No	xxxxx	xxxxx	xxxxx	xxxxx	xxxxx	Death DDMMYYYY
		xxxxxx	xxxxxx	xxxxxx	xxx	Yes	DDMMYYYY	DDMMYYYY	No	xxxxx	xxxxx	xxxxx	xxxxx	xxxxx	xxxxx
xxx	xxx	xxxxxx	xxxxxx	xxxxxx	xxx	No	DDMMYYYY	DDMMYYYY	No	xxxxx	xxxxx	xxxxx	xxxxx	xxxxx	xxxxx
		xxxxxx	xxxxxx	xxxxxx	xxx	No	DDMMYYYY		Yes	xxxxx	xxxxx	xxxxx	xxxxx	xxxxx	xxxxx

(1) SAE: No, Yes, UNK

(2) Ongoing: No, Yes, UNK

(3) Duration= End Date - Start Date + 1; Duration =Date of Last Dose - Start Date + 1 if AE is ongoing

(4) Severity: 1= Mild, 2= Moderate, 3= Severe, 4= Life-threatening, 5= Death, UNK

(5) Relationship: Not related, Possibly, Probably, UNK

(6) Action Taken: None, Treatment required, Study drug dose reduction, Study drug dose discontinued & restarted, Study drug permanently discontinued, UNK

(7) Outcome: Resolved, Resolved w/sequelae, Not resolved, Death, UNK

(8) Seriousness: Fatal, Life threatening, Hospitalization, Persistent disability, Congenital anomaly, Important medical Event, UNK

Source: [program name].sas, Run on ddmmmyyyy.

Programming Notes: Sort by site, patient number and start date.

Listing 16.2.5.2. Treatment Emergent Serious Adverse Events

Site	Patient	SOC	PT	Verbatim Term	SAE (1)	Start date	End date	Ongoing (2)	Duration (3)	Severity (4)	Relationship (5)	Action taken (6)	Outcome (7)	Date of death	Seriousness (8)
xxx	xxx	xxxxxx	xxxxxx	xxxxxx	xxx	DDMMYYYY	DDMMYYYY	No	xxxxx	xxxxx	xxxxx	xxxxx	xxxxx	xxxxx	xxxxx
		xxxxxx	xxxxxx	xxxxxx	xxx	DDMMYYYY		Yes	xxxxx	xxxxx	xxxxx	xxxxx	xxxxx	xxxxx	DDMMYYYY
		xxxxxx	xxxxxx	xxxxxx	xxx	DDMMYYYY	DDMMYYYY	No	xxxxx	xxxxx	xxxxx	xxxxx	xxxxx	xxxxx	xxxxx
xxx	xxx	xxxxxx	xxxxxx	xxxxxx	xxx	DDMMYYYY	DDMMYYYY	No	xxxxx	xxxxx	xxxxx	xxxxx	xxxxx	xxxxx	xxxxx
		xxxxxx	xxxxxx	xxxxxx	xxx	DDMMYYYY		Yes	xxxxx	xxxxx	xxxxx	xxxxx	xxxxx	xxxxx	xxxxx

(1) SAE: No, Yes, UNK

(2) Ongoing: No, Yes, UNK

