xxx	xxx	xxxxxx	xxxxxx	xxxxxx	xxx	No	DDMMYYYY	DDMMYYYY	No	xxxxx	xxxxx	xxxxx	xxxxx	xxxxx	xxxxx	xxxxx	xxxxx
		xxxxxx	xxxxxx	xxxxxx	xxx	No	DDMMYYYY		Yes	xxxxx	xxxxx	xxxxx	xxxxx	xxxxx	xxxxx	DDMMYYYY	xxxxx
		xxxxxx	xxxxxx	xxxxxx	xxx	Yes	DDMMYYYY	DDMMYYYY	No	xxxxx	xxxxx	xxxxx	xxxxx	xxxxx	xxxxx		xxxxx
xxx	xxx	xxxxxx	xxxxxx	xxxxxx	xxx	No	DDMMYYYY	DDMMYYYY	No	xxxxx	xxxxx	xxxxx	xxxxx	xxxxx	xxxxx		xxxxx
		xxxxxx	xxxxxx	xxxxxx	xxx	No	DDMMYYYY		Yes	xxxxx	xxxxx	xxxxx	xxxxx	xxxxx	xxxxx		xxxxx

(1) SAE: No, Yes, UNK

(2) Ongoing: No, Yes, UNK

(3) Duration= End Date - Start Date + 1; Duration =Date of Last Dose - Start Date + 1 if AE is ongoing

(4) Severity: 1= Mild, 2= Moderate, 3= Severe, 4= Life-threatening, 5= Death, UNK

(5) Relationship: Not related, Possibly, Probably, UNK

(6) Action Taken: None, Treatment required, Study drug dose reduction, Study drug dose discontinued & restarted, Study drug permanently discontinued, UNK

(7) Outcome: Resolved, Resolved w/sequelae, Not resolved, Death, UNK

(8) Seriousness: Fatal, Life threatening, Hospitalization, Persistent disability, Congenital anomaly, Important medical Event, UNK

Source: [program name].sas, Run on ddmmmyyyy.

Programming Notes: Sort by site, patient number and start date.

Listing 16.2.6.1. Clinical Laboratory Evaluations: Blood Chemistry

Site	Patient	Visit	Blood sample taken?	Sample date	Laboratory parameter	Original Unit				Standard Unit (SI)			
						Values	Unit (1)	NRLL	NRUL	Clinical assessment (2)	Assessment respect to Normal Ranges (3)		
											Value	Unit	CFB
xxx	xxx	Screening	xxx	DDMMYYYY	Albumin	xxx	xxx	xxx	xxx	xxx	xxx	xxx	xxx
					Alkaline Phosphatase	xxx	xxx	xxx	xxx	xxx	xxx	xxx	xxx
					ALT	xxx	xxx	xxx	xxx	xxx	xxx	xxx	xxx
					AST	xxx	xxx	xxx	xxx	xxx	xxx	xxx	xxx
					...								
		Month 3	No		Albumin								
					Alkaline Phosphatase								
					ALT								
					AST								
					...								
		...	xxx	DDMMYYYY	Albumin	xxx	xxx	xxx	xxx	xxx	xxx	xxx	xxx
					Alkaline Phosphatase	xxx	xxx	xxx	xxx	xxx	xxx	xxx	xxx
					ALT	xxx	xxx	xxx	xxx	xxx	xxx	xxx	xxx
					AST	xxx	xxx	xxx	xxx	xxx	xxx	xxx	xxx
					...								
		EOS	xxx	DDMMYYYY	Albumin	xxx	xxx	xxx	xxx	xxx	xxx	xxx	xxx
					Alkaline Phosphatase	xxx	xxx	xxx	xxx	xxx	xxx	xxx	xxx
					ALT	xxx	xxx	xxx	xxx	xxx	xxx	xxx	xxx
					AST	xxx	xxx	xxx	xxx	xxx	xxx	xxx	xxx

CFB=Change from Baseline.

NRLL: Normal Range Lower Limit; NRUL: Normal Range Upper Limit.

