Programming Notes: Continue for other body system: throat, cardiovascular, dermatologic, lymphatic, respiratory, gastrointestinal, musculoskeletal and other. Sort by site, patient number and visit.

Listing 16.2.8. Concomitant Medications

Site	Patient	Patient receive medication?	#	Total daily dose	Units	Route	If Other Route, specify	Start date	End date	Ongoing at end of study?	Reason for administration	Indication for use
(1)			Generic name	(2)							(3)	
xxx	xxx	xxx	x xxxxxxxxx	xxxx	xxxxx	xxxx	xxxxxx	DDMMYYYY	DDMMYYYY	No	xxxxxxxxxx	xxxxxxxxxx
			x xxxxxxxxx	xxxx	xxxxx	xxxx	xxxxxx	DDMMYYYY		Yes	xxxxxxxxxx	xxxxxxxxxx
xxx	xxx	xxx	x xxxxxxxxx	xxxx	xxxxx	xxxx	xxxxxx	DDMMYYYY	DDMMYYYY	No	xxxxxxxxxx	xxxxxxxxxx
			x xxxxxxxxx	xxxx	xxxxx	xxxx	xxxxxx	DDMMYYYY	DDMMYYYY	No	xxxxxxxxxx	xxxxxxxxxx
			x xxxxxxxxx	xxxx	xxxxx	xxxx	xxxxxx	DDMMYYYY	DDMMYYYY	No	xxxxxxxxxx	xxxxxxxxxx
xxx	xxx	No										

(1) Did the patient receive Previous and/or Concomitant medications?

(2) Route: PO, IM, IV, SC, Rectal, Topical, Nasal, Inhaled, Other, UNK

(3) Reason for administration?: Therapeutic, Prophylaxis, Other, AE treatment, UNK

Source: [program name].sas, Run on ddmmmyyyy.

Programming Notes: Sort by site, patient number and start date.

Listing 16.2.9. End of Study

Site	Patient	End of study assessment date	Did the patient take at least one dose of study medication?	Date of last study drug dose intake	Complete the treatment? (1)	If No, report the primary reason for discontinuation	If reason is AE, Major Protocol Deviation, or Other Reason, specify	If reason is Consent Withdrawal, specify the date
xxx	xxx	DDMMYYYY	xxx	DDMMYYYY	Yes			
xxx	xxx	DDMMYYYY	xxx	DDMMYYYY	Yes			
xxx	xxx	DDMMYYYY	No		No	Consent Withdrawal		DDMMYYYY
xxx	xxx	DDMMYYYY	xxx	DDMMYYYY	No	Adverse event	Xxxxxxxxxx	
xxx	xxx	DDMMYYYY	xxx	DDMMYYYY	No	xxxxxxxxxx		

(1) Did the patient complete the full course of treatment?

Source: [program name].sas, Run on ddmmmyyyy.

Programming Note: Sort by site and patient number.

Listing 16.2.10. Comments

Site	Patient	Presence of comments?	Visit (1)	Form (2)	Comment
xxx	xxx	xxx	xxx	xxx	XXXXXXXXXXXX
xxx	xxx	xxx	xxx	xxx	XXXXXXXXXXXX
xxx	xxx	xxx	xxx	xxx	XXXXXXXXXXXX
xxx	xxx	xxx	xxx	xxx	XXXXXXXXXXXX
xxx	xxx	xxx	xxx	xxx	XXXXXXXXXXXX

(1) Visit: Screening, End of study month 3, End of study month 6, End of study month 9, End of study month 12, End of study month 15, End of study month 21, End of study month 27, EoS, Extra visit

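### The AE listings end the duration of a still-ongoing event at the last dose, so that value can be too short, zero or negative: a minor error in one derived column

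*SAP*

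**What the plan says.** Footnote (3) to SAP Listing 16.2.5.1 runs an event that has ended from its start date to its end date, counting both days. For an event that has not ended it sets "Duration =Date of Last Dose - Start Date + 1 if AE is ongoing". The same footnote stands under the other eight AE listings, up to 16.2.5.9. SAP 10.12.1 gives no other rule for duration, and nothing in the SAP labels the value as on-treatment time or as censored.

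The documents set these limits on which events are recorded and for how long:

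- SAP 10.12.1 defines a TEAE as "any AE that emerges after the first dose of study drug for the current Long-Term Study". There is no upper limit relative to the last dose.
- Protocol 11.2 says that the SAE reporting period "continues through 4 weeks after the last visit".
- Protocol 11.1 has ongoing non-serious AEs reported "through the termination visit or at the early termination visit".
- SAP 10.12.1, like Protocol 11.1, adds: "The Investigator should follow all unresolved AEs until the events are resolved or stabilized". The stated exceptions are loss to follow-up and a finding that the study is not the cause.

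On how the last dose relates to the last visit, Protocol Table 1 states: "End of Study is the patients last visit to the site and discontinuation of study medication". Protocol 10.2.3, however, treats withdrawal from study drug and withdrawal from the study as separate events and gives no maximum gap between them. SAP Listing 16.2.9 has a column headed "End of study assessment date", separate from the column for the date of last dose.

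**The concern.** The rule closes an open event at a date that data collection does not respect. Follow-up after the last dose is lost from the duration, and an open event that began after the last dose gets a value that no duration can take.

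Listing 16.2.5.7, on TEAEs leading to premature discontinuation, is the most exposed. When an event causes the drug to be stopped, the cut-off falls close to onset, so an unresolved event can be listed as lasting a day or two. The primary objective is long-term safety and tolerability in about 12 patients, so readers will look at individual rows.

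**Working it through.** The plan states no figure to reproduce. The check is date arithmetic on the footnote.

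**Inputs.** The duration rule comes from footnote (3). The 28 days (4 weeks) after the last visit come from Protocol 11.2. The gap g from last dose to last visit is not given in the documents, so I assume 0, 7, 30 and 90 days to show a range.

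**Formulas.** Count days from the last dose (day 0). Let s be the onset day and c the day of last contact.

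- Listed duration of an ongoing event: 0 − s + 1 = 1 − s.
- Duration observed to last contact: c − s + 1.
- Shortfall: (c − s + 1) − (1 − s) = c, the time from last dose to last contact, whatever the onset.

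If last dose and last visit coincide and nothing later is recorded, c = 0 and there is no shortfall.

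**Last dose at the last visit, event still open 28 days later (g = 0, c = 28):**

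| Onset relative to last dose | Listed (1 − s) | Observed so far (29 − s) |
|---|---|---|
| 30 days before | 31 | 59 |
| same day | 1 | 29 |
| 1 day after | 0 | 28 |
| 2 days after | −1 | 27 |
| 14 days after | −13 | 15 |
| 28 days after | −27 | 1 |

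**Drug stopped before the last visit (c = g + 28).** An SAE that starts on the day of last dose and is still open at the end of reporting is listed as 1 day. The observed duration is g + 29, which is 29, 36, 59 or 119 days for g = 0, 7, 30 or 90. An open SAE that starts on the last day of the reporting period is listed as 1 − (g + 28), which is −27, −34, −57 or −117.

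**Two definitions in one column (hypothetical days).** Both events start on day 100, and the last dose is on day 101.

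- Resolved on day 111: listed as 111 − 100 + 1 = 12 days.
- Unresolved at a contact on day 129: listed as 101 − 100 + 1 = 2 days, though 129 − 100 + 1 = 30 days have been observed.

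The event that lasted longer is listed as the shorter one.

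**Listing 16.2.5.9.** These events start before the first dose, and so before the last. The value is always positive and can only be too short. For an enrolled patient who was never dosed it cannot be computed.

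**The case against.** The strongest defence is that the column is meant as on-treatment duration. The footnote does not bear this out: it runs a resolved event to its end date even when that date falls after the last dose.

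Other points on the sponsor's side stand:

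- The last-dose rule applies only to events still flagged as ongoing. A reader might infer that every event starting after the last dose gets a zero or negative duration. The documents do not support that: an event with an end date is computed correctly, and the follow-up rule should supply many end dates.
- For patients who stop drug at the end of study visit, non-serious AE reporting ends at that visit. There, a zero or negative value would normally need an SAE that starts in the following 4 weeks and stays unresolved. A wider gap is possible for earlier stoppers, but the documents do not say how wide or how often.
- A reader might infer that an unresolved toxicity would pass as a brief one. The same row prints the start date, an empty end date, the ongoing flag, the action taken with study drug and the outcome, so the event is still visibly unresolved. The date of last dose is not in that row, though; it is in Listing 16.2.9.
- A reader might also infer that the safety results are biased. Protocol section 3 assesses safety by TEAE incidence, and none of the ten AE summary tables in SAP 10.12.1 uses duration.
- SAP section 4 already foresees that shells and mock listings may be revised before the final analysis.

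These points limit the consequence. They do not make the formula right.

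**Conclusion.** The point holds for AEs still ongoing at database lock. Their listed duration is short by the time from last dose to last contact, and it is zero or negative when onset follows the last dose (Listing 16.2.5.9 excepted). The size depends on the patient: about nil when last dose and last visit coincide and nothing later is recorded, and 28 days plus any gap to the last visit for an SAE still open at the end of reporting. The gaps used above are assumptions and the day-numbered example is hypothetical.

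Events with an end date are unaffected. Incidence, severity, relationship and seriousness results do not change. This is a minor error in one derived listing column, but the rule is wrong as written, and it can put an unresolved event and a resolved one in the wrong order of length.

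**What to change.** In footnote (3) of Listings 16.2.5.1 to 16.2.5.9, replace the last-dose cut-off for ongoing events with the later of the end of study assessment date (Listing 16.2.9) and the last recorded AE or SAE follow-up date, or with the date of death where the patient died. Print the result as a censored value, for example ≥ x days, ongoing. If the only cut-off available falls before onset, as it could for an SAE that starts after the last visit, leave the duration blank. The minimum acceptable change is a blank duration with status ongoing for every open event.

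The cost is one shared footnote and one derivation in the listing programs. The end of study assessment date and the date of death are already planned listing fields. Whether a dated contact for the 4-week SAE period is captured cannot be told from the documents, because the CRF is not among them. That part depends on what the SAE records hold.
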